#### **7.12 Study Intervention/Follow-up Compliance**

Subject will be asked to complete a log documenting the date and time that the study medication is taken (every other day).

Pill counts will be done at each visit.

If necessary, 3 attempts will be made to get subject to return for study follow-up Appointments. If the patient does not respond to 3 attempts he/she will be considered "lost to follow-up" and no longer participating in the study.

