## 8.2 Participant Discontinuation/Withdrawal from the Study

Participants are free to withdraw from participation in the study at any time upon request. An investigator may discontinue or withdraw a participant from the study for the following reasons:

1. Pregnancy. However, subjects will be followed until the end of the pregnancy.
2. Significant study intervention non-compliance (failure to take medications, refuses to allow study procedures).
3. Participant lost to follow-up after 3 attempts to contact subject to schedule study visit.

The reason for participant discontinuation or withdrawal from the study will be recorded on the Case Report Form (CRF). Subjects who sign the informed consent form and are randomized but do not receive the study intervention may be replaced. Subjects who sign the informed consent form, and are randomized and receive the study intervention, and subsequently withdraw, or are withdrawn or discontinued from the study will not be replaced.

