## 8.3 Lost to Follow Up

A participant will be considered lost to follow-up if he or she fails to return for a scheduled visit and is unable to be contacted by the study site staff.

The following actions must be taken if a participant fails to return to the clinic for a required study visit:

- The site will attempt to contact the participant and reschedule the missed visit within 2 days and counsel the participant on the importance of maintaining the assigned visit schedule and ascertain if the participant wishes to and/or should continue in the study.

- Before a participant is deemed lost to follow-up, the investigator or designee will make every effort to regain contact with the participant (where possible, 3 telephone calls). These contact attempts should be documented in the participant's medical record or study file.
- Should the participant continue to be unreachable, he or she will be considered to have withdrawn from the study with a primary reason of lost to follow-up.

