### **12.4 Analysis of Endpoints**

#### **12.4.1 Analysis of Primary Endpoints**

The primary endpoint is the week 16 PASI score. We will calculate the percent reduction in week 16 PASI scores post treatment from baseline. Summary statistics in terms mean, standard deviation, median and range or inter-quartile range will be generated for each study arm. Between treatment arm differences will be evaluated using a two-sample t-test or the non-parametric Wilcoxon rank sum test where appropriate. The primary analysis will be carried out on an intention-to-treat basis. Last value carried forward will be used to impute for patients missing week 16 measurements. Per-protocol analysis will also be carried out among patients who are deemed compliant to treatment (defined as at least 75% of doses taken as measured by pill counts) and had both baseline and week 16 measurements will also be carried out using similar statistical methods. P-values less than 0.05 will be considered statistical significant.

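### A subject is classed as lost and withdrawn after one missed visit and failed contact, with no planned further attempt at week 16, which can leave avoidable gaps in the primary endpoint

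*Combined protocol and SAP*

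**What the plan says.** Three protocol sections govern a subject who stops attending.

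- Section 7.12: "If the patient does not respond to 3 attempts he/she will be considered 'lost to follow-up' and no longer participating in the study".
- Section 8.3 sets the trigger: "A participant will be considered lost to follow-up if he or she fails to return for a scheduled visit and is unable to be contacted". The site tries to rebook the missed visit within 2 days and must make "every effort to regain contact with the participant (where possible, 3 telephone calls"). If that fails, "he or she will be considered to have withdrawn from the study with a primary reason of lost to follow-up".
- Section 8.2 says "An investigator may discontinue or withdraw a participant from the study for the following reasons", and item 3 reads "Participant lost to follow-up after 3 attempts to contact subject to schedule study visit". Subjects who have received study drug and then withdraw are not replaced.

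Section 12.4.1 makes the percent reduction in PASI at week 16 the primary comparison, by intention to treat, and adds: "Last value carried forward will be used to impute for patients missing week 16 measurements". Section 12.6.2 limits the assessment of response to subjects with at least 4 weeks of treatment. PASI is scored at baseline and every 2 weeks to week 20 (Sections 1.2.4 and 6.1).

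**The concern.** The primary endpoint uses one visit, week 16. The lost status can be assigned at any visit from week 2 on, up to 14 weeks earlier. The three attempts have no minimum spread, so they could all fall within a few days of the missed visit. Once the status is assigned, nothing tells the site to try again when week 16 comes round, and nothing tells the analyst what to do with a PASI from a subject who reappears.

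Staff who follow the text as written may therefore stop pursuing a subject who was only briefly out of reach. An early score, or baseline itself, then stands in for the week 16 result. With about 15 subjects per arm, one or two such cases per arm are enough to move the estimate. If losses differ between arms, the error can go in either direction.

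**Working it through.** **Inputs from Section 12.2.** 15 per arm, effect size 1.06, SD 20 percentage points, two-sided 0.05, two-sample t-test, stated power 80%, dropout allowance 25%.

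**Reproducing the plan's figure.** Noncentral t with 28 degrees of freedom and effect size 1.06 gives power 0.800. The difference is 1.06 × 20 = 21.2 points. The plan's figure holds.

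**Earliest value carried forward.** A subject lost at the missed week 4 visit has week 2 as the last PASI. A subject lost at the missed week 2 visit has only baseline, so the percent reduction is 0. Section 12.6.2 might remove a subject with under 4 weeks of treatment, but Section 12.4.1 calls for intention to treat, and the plan does not say which governs.

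**Assumptions not in the documents.** The true week 16 difference is 21.2, the effect grows linearly to week 16, the SD stays at 20, and k of 15 per arm are closed out, all at the same visit.

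**Carry-forward from week w.** Expected difference = 21.2 × [1 − (1 − w/16) × k/15].

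| k per arm | Last value | Difference | Power |
|---|---|---|---|
| 2 | baseline | 18.37 | 68.0% |
| 2 | week 2 | 18.73 | 69.7% |
| 2 | week 4 | 19.08 | 71.3% |
| 2 | week 12 | 20.49 | 77.3% |
| 1 | week 2 | 19.96 | 75.1% |
| 1 | week 4 | 20.14 | 75.9% |

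**The same 2 of 15 per arm measured at week 16.** If they keep a fraction r of the effect, difference = 21.2 × [1 − (1 − r) × 2/15].

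| r | Difference | Power |
|---|---|---|
| 1 | 21.20 | 80.0% |
| 0.5 | 19.79 | 74.4% |
| 0.25 | 19.08 | 71.3% |

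The cost of the rule is the gap between the two tables. With full effect kept it is about 9 to 12 points of power (80.0 − 71.3 = 8.7; 80.0 − 68.0 = 12.0). With half kept it is about 3 to 6 points (74.4 − 71.3 = 3.1; 74.4 − 68.0 = 6.4). With a quarter kept, carrying week 4 forward costs nothing.

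**Unequal loss.** Assume week 16 mean reductions of 36.2 and 15, with lost subjects carried forward from halfway.

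- 3 lost on rimegepant, 1 on placebo: 36.2 × (1 − 0.5 × 3/15) − 15 × (1 − 0.5 × 1/15) = 32.58 − 14.50 = 18.1.
- 1 lost on rimegepant, 3 on placebo: 36.2 × (1 − 0.5 × 1/15) − 15 × (1 − 0.5 × 3/15) = 34.99 − 13.50 = 21.5.

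Against a true 21.2, the error takes either sign.

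**The case against.** A reader might infer that the rule shuts a subject out permanently. The documents do not say that. Re-entry and later contact are not mentioned and not forbidden, Section 8.2 says the investigator may withdraw a subject, and Section 8.3 asks for every effort first. Section 12.4.1 imputes only when the week 16 value is missing, so on its wording a PASI actually obtained would not be replaced. What stands is that Sections 7.12 and 8.3 assign the status in firm terms and leave the site without an instruction to call again.

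A reader might also see a contradiction with Section 8.1, which keeps subjects who stop drug under assessment to week 20. There is none: Section 8.1 covers subjects who can still be seen, and Section 8.3 covers those who cannot be reached.

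The strongest objection concerns size. Drug is dispensed at Day 0 and week 8, as 30 tablets or 32 ODTs each time (Section 7.7), which lasts 60 to 64 days on alternate-day dosing. A subject out of contact from week 4 to week 16 (day 112) misses the second supply, so full effect at week 16 is not a fair assumption for that subject. This stands, and it makes the comparison with 80% close to an upper bound.

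Loss is also partly planned for. Section 12.2 allows 25% dropout and recruits 45, although the Protocol Summary says 30; that conflict is a separate matter. With 22 per arm, 2 per arm carried forward from week 2 or week 4 leaves 88.5% or 89.2% power. The illustrated shortfall below 80% therefore applies only if 30 are enrolled. The longitudinal mixed models in Section 12.4.2 use no imputation, but they are not the primary analysis.

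Finally, much of the possible bias comes from carrying values forward rather than from the contact rule. That is true, but fewer missing week 16 values would limit it.

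**Conclusion.** The point holds as a correctable weakness in follow-up. One missed visit with failed contact (three attempts, where possible) is enough for withdrawn status. No minimum period is set for the attempts, no attempt at week 16 is planned, and the use of a later PASI is not addressed. This can create missing primary outcomes that another call might have avoided, with baseline as the earliest value carried forward unless Section 12.6.2 excludes the subject.

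The size cannot be determined, because the documents give no return rate and the 25% allowance covers dropout in general. The illustrated cost at 15 per arm, with 2 per arm closed out early, runs from about 3 to 6 points of power if half the effect is kept to about 9 to 12 if all of it is kept. It is smaller for later losses and vanishes if little effect remains. These figures rest on linear onset, a fixed SD and the return of every such subject. They support a low-cost improvement and do not show that the trial is underpowered because of this rule.

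**What to change.** In Section 7.12, Section 8.2 item 3 and Section 8.3:

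- Record a missed visit with three failed contacts as a missed visit, not as withdrawal.
- Repeat the contact attempts at each later scheduled visit, and specifically for week 16.
- Assign the lost-to-follow-up status only if there has been no contact by the close of the week 20 window.

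In Sections 12.4.1 and 12.4.2, state that any PASI, IGA, DLQI and itch score obtained from a subject who returns enters the intention-to-treat analysis. State also whether baseline may be carried forward, and how Section 12.6.2 fits with intention to treat. Whether study drug continues stays under the existing treatment sections.

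The cost is protocol wording, a few extra calls per unreachable subject, and records that stay open until week 20.

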### **8. Study Intervention Discontinuation and Participant Discontinuation/Withdrawal**

#### **8.1 Discontinuation of Study Intervention**

Subjects will be withdrawn from study treatment permanently for the following reasons:

1. Development of any hypersensitivity phenomena that may be related to the study medication.
2. Excessive nausea making continuation of participation in the study impossible.
3. Development of any intercurrent illness or medical need to take a medication such that exclusion criteria apply.
4. Occurrence of pregnancy in a female subject.
5. If any clinical adverse event (AE), laboratory abnormality, or other medical condition or situation occurs such that continued participation in the study would not be in the best interest of the participant
6. Disease progression which requires discontinuation of the study intervention
7. If the participant meets an exclusion criterion (either newly developed or not previously recognized) that precludes further study participation

Subjects will be referred for appropriate medical care for any adverse effects.

Subjects will continue to be followed for assessment of disease severity until the 20-week period is over.

Discontinuation of treatment does not mean discontinuation from the study, and remaining study procedures (assessments of disease severity) will be completed as indicated by the study protocol.

If a clinically significant finding is identified (including, but not limited to changes from baseline) after enrollment, the investigator or qualified designee will determine if any change in participant management is needed. Any new clinically relevant finding will be reported as an adverse event (AE).

**Criteria for interrupting the study:** We will have a study monitoring committee (SMC) consisting of the study PI, the medical monitor and 1 investigator not directly involved in the conduct of this study. This committee will review all Grade 3 or 4 events, and all SAEs in real time. We will pause enrollment of new participants if there is 1 or more Serious Adverse Events that are at least possibly related to study drug, or 2 or more Grade 3 or 4 events at least possibly related to study drug. The enrollment of participants will not resume until the SMC reviews the adverse events and agrees unanimously to resume enrollment.

## 8.2 Participant Discontinuation/Withdrawal from the Study

Participants are free to withdraw from participation in the study at any time upon request. An investigator may discontinue or withdraw a participant from the study for the following reasons:

1. Pregnancy. However, subjects will be followed until the end of the pregnancy.
2. Significant study intervention non-compliance (failure to take medications, refuses to allow study procedures).
3. Participant lost to follow-up after 3 attempts to contact subject to schedule study visit.

The reason for participant discontinuation or withdrawal from the study will be recorded on the Case Report Form (CRF). Subjects who sign the informed consent form and are randomized but do not receive the study intervention may be replaced. Subjects who sign the informed consent form, and are randomized and receive the study intervention, and subsequently withdraw, or are withdrawn or discontinued from the study will not be replaced.

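### Section 8.2 lets the investigator end a subject's follow-up for not taking study medication, so an obtainable week 16 PASI may be replaced by a carried-forward value

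*Combined protocol and SAP*

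**What the plan says.** Protocol Section 8.2 introduces its list with a permission: "An investigator may discontinue or withdraw a participant from the study for the following reasons". The second reason is "Significant study intervention non-compliance (failure to take medications, refuses to allow study procedures". What makes non-compliance significant is not defined. The section adds that subjects who were randomised and treated and who "subsequently withdraw, or are withdrawn or discontinued from the study will not be replaced".

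Section 8.1 deals with stopping study treatment. It gives seven numbered reasons, and non-adherence is not one of them. It then states a general rule, "Discontinuation of treatment does not mean discontinuation from the study, and remaining study procedures (assessments of disease severity) will be completed", and gives the duration: "Subjects will continue to be followed for assessment of disease severity until the 20-week period is over".

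Section 12.4.1 says "The primary analysis will be carried out on an intention-to-treat basis". A missing week 16 PASI is filled with the last value carried forward. Section 12.4.2 plans imputation of that kind for the week 16 changes in the secondary scores. Adherence has its own analysis, a per-protocol set with compliance "defined as at least 75% of doses taken as measured by pill counts" and with both baseline and week 16 measurements required.

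No section says that PASI is still assessed once a subject has been withdrawn under Section 8.2.

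**The concern.** An intention-to-treat analysis depends on collecting the outcome whether or not the subject took the drug. Section 8.1 follows that principle. Section 8.2 allows the opposite for one group: subjects who do not take their medication can be taken out of the study, not only off treatment, on the investigator's judgement.

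A subject who still attends can have PASI scored at week 16. If that subject is withdrawn, the visit does not happen and Section 12.4.1 substitutes an older score. This missing value is avoidable, and it may be informative, because adherence is a post-randomisation event that can be related to how the subject is doing. Withdrawn treated subjects are not replaced and the arms are small, so each lost value counts.

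**Working it through.** **1. The plan's own figure.** Inputs from Section 12.2: 15 per arm, effect size 1.06, standard deviation of percent PASI reduction 20 points, two-sample t-test, two-sided 0.05. With 28 degrees of freedom the noncentrality is 1.06 × √(15/2) = 2.90, and the noncentral t distribution gives power 0.800. The stated 80% reproduces. The target difference is 1.06 × 20 = 21.2 points. This point does not question that calculation; it uses only the 15 per arm and the SD.

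**2. The sections side by side.**
- A subject taken off drug for a reason listed in Section 8.1, such as excessive nausea, is assessed to week 20.
- A subject who skips doses, for that or any other reason, may be withdrawn from the study under Section 8.2. Nothing then provides for a week 16 PASI.
- Section 7.9 is headed as covering removal from the study, yet its criteria are those that end treatment. Section 7.10 speaks of subjects removed from the study for adverse events, and sets follow-up at 4 weeks after the drug is stopped. Read literally, a subject stopping at week 6 is followed to week 6 + 4 = 10. Only a stop at week 12 or later reaches week 16 (12 + 4 = 16). Section 8.1 would follow both to week 20.
- Pregnancy appears in both the 8.1 and the 8.2 lists, so the same event leads to two statements about follow-up.

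**3. What replaces the missing score.** PASI is scheduled every 2 weeks (Section 6.1). A subject withdrawn after the week 4 visit would enter the primary analysis with the week 4 score standing for week 16, a gap of 12 weeks.

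**4. Illustration of size.** Let g be the difference between the carried-forward and the true week 16 percent reduction. One such subject shifts the arm mean by g / n.
- Assumption: g = 20 to 40 points, which is 1 to 2 of the plan's SDs. The documents give no value.
- With n = 15: 20/15 = 1.33 and 40/15 = 2.67 points.
- Section 12.2 also says 45 will be recruited, against 30 in Section 1. With 45/2 = 22.5 per arm the shift is 20/22.5 = 0.9 to 40/22.5 = 1.8 points. That mismatch is a separate matter.
- For scale, the standard error of the difference in means at 15 per arm is 20 × √(2/15) = 7.3 points.

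**5. What cannot be calculated.** The documents give no non-adherence rate, no expected PASI course after doses are missed, and no indication of how often the Section 8.2 permission would be used. A non-adherent subject who is kept may also show a reduced effect at week 16, so even the direction of the change from better follow-up is not determined.

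**The case against.** The strongest reply is that Sections 8.1 and 8.2 describe two pathways, stopping treatment and leaving the study, and that a rule for one does not negate a rule for the other. A reader might infer a flat contradiction. The documents do not support that: non-adherence is not among the 8.1 reasons, and 8.2 only permits withdrawal. What stands is an inconsistency with 8.1's general follow-up principle.

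A reader might also infer that withdrawn subjects drop out of the intention-to-treat set. They do not, because last value carried forward keeps them in. The tension is with collecting outcomes regardless of adherence.

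It is tempting to say that removal will differ by arm, through nausea on active drug or lack of benefit on placebo. This is possible but not shown. The only nausea rates given (Section 2.4.1, from the package insert) are 2% and 0.4%, or 15 × 0.02 = 0.3 and 15 × 0.004 = 0.06 subjects per arm. Excessive nausea and disease progression requiring discontinuation are also both 8.1 reasons, with follow-up continued.

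Expressing the shift as a share of the 21.2-point target would need several withdrawals in one arm, with errors in the same direction and none in the other arm. Nothing in the documents supports that pattern.

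Finally, the per-protocol set is an analysis filter and Section 8.2 is a conduct rule, so one does not make the other redundant. That is fair. But the per-protocol set does mean that the analysis has no need for non-adherent subjects to leave the study. For subjects who refuse procedures, the week 16 PASI may be unobtainable under any wording.

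**Conclusion.** The point holds in limited form. Section 8.2 permits, with no threshold, investigator-initiated withdrawal from the study for not taking medication, and no section preserves outcome assessment afterwards. A willing subject could therefore lose an obtainable week 16 PASI and be analysed on an earlier value. This is avoidable and possibly informative missing data in the primary analysis.

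The loss is possible rather than certain, and neither its bias nor any dependence on arm can be derived. The shift of 1.3 to 2.7 points in an arm mean per affected subject rests on 15 per arm and an assumed 20 to 40 point gap. It is below one standard error of the difference (7.3 points). This is a worthwhile, inexpensive improvement, not a flaw that invalidates the design.

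**What to change.** - In Section 8.2, remove not taking study medication as a ground for the investigator to withdraw a subject from the study.
- State that non-adherent subjects who remain willing continue the scheduled PASI, IGA, DLQI and itch assessments through week 20, are analysed as randomised, and are excluded only from the per-protocol set.
- Leave withdrawal by the subject, and refusal of procedures, as they are.
- Reconcile Sections 7.9, 7.10, 8.1, 8.2 and 12.4.1 on whether outcome assessments continue after treatment stops, including the event listed in both 8.1 and 8.2. Check Section 12.6.2 at the same time, since its requirement of at least 4 weeks of treatment for response assessment bears on analysis as randomised.

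The change concerns outcome collection and analysis only; it takes no position on when study medication should be stopped. The cost is a few lines of protocol wording and the completion of already scheduled visits for a few non-adherent subjects.

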## 8.3 Lost to Follow Up

A participant will be considered lost to follow-up if he or she fails to return for a scheduled visit and is unable to be contacted by the study site staff.

The following actions must be taken if a participant fails to return to the clinic for a required study visit:

- The site will attempt to contact the participant and reschedule the missed visit within 2 days and counsel the participant on the importance of maintaining the assigned visit schedule and ascertain if the participant wishes to and/or should continue in the study.

- Before a participant is deemed lost to follow-up, the investigator or designee will make every effort to regain contact with the participant (where possible, 3 telephone calls). These contact attempts should be documented in the participant's medical record or study file.
- Should the participant continue to be unreachable, he or she will be considered to have withdrawn from the study with a primary reason of lost to follow-up.

